# 1. Statistical Analysis Plan

## 1.1 Study type

This study is a community-based clustered randomized controlled trial. The study design (**Figure 4- 1**) is shown as follows:

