## **1.5 Sample size calculation**

Sample size estimation will be conducted based on literature review and empirical data from our national program. We are assuming colorectal cancer detection rate of 2.4/1000 by one-sample FIT and 4.8/1000 by two-sample FIT with a FIT screening uptake rate of 60% in both arms, 80% power and one-tail significant level at 0.05, also taking into account cluster size of 65 (The total number of townships in Changhua, Tainan and Kaohsiung) with inter-cluster correlation coefficient of 0.01, the estimated sample size is 14,625 subjects for each arm.

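### The 14,625 per arm does not follow from the stated inputs: with 65 townships in total and ICC 0.01, power is about 40% and 80% is out of reach at any enrolment

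*SAP*

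**What the plan says.** SAP section 1.5 is the only justification of sample size in the documents. Its inputs are:

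- a "colorectal cancer detection rate of 2.4/1000 by one-sample FIT and 4.8/1000 by two-sample FIT";
- a "FIT screening uptake rate of 60% in both arms";
- "80% power and one-tail significant level at 0.05";
- a "cluster size of 65 (The total number of townships in Changhua, Tainan and Kaohsiung) with inter-cluster correlation coefficient of 0.01".

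It concludes that "the estimated sample size is 14,625 subjects for each arm". No formula or design effect is shown.

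On the design, section 1.1 states: "This study is a community-based clustered randomized controlled trial". Sections 1.3 and 1.4 also call the trial cluster-randomized. Section 1.4 lists four groups (one- or two-day sampling, crossed with a one- or two-year interval), while section 1.6 describes two arms, one-day and two-day sampling.

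**The concern.** Cluster size and number of clusters enter a design-effect calculation in different places, and section 1.5 uses one number for both. If 65 is the number of townships in the whole trial, each arm has about 32 with two arms, or about 16 with four. An ICC of 0.01 is then a heavy penalty. With K clusters per arm, the effective sample size per arm can never exceed K/ICC, whatever the enrolment.

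What is at stake is how the result will be read. A trial planned on a claimed 80% power that is really near 40% would more often than not miss a true doubling of the detection rate. A null result could then be taken as evidence that two-day sampling adds nothing.

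**Working it through.** **Inputs (SAP section 1.5).** p1 = 0.0024, p2 = 0.0048, one-sided alpha 0.05 (z = 1.645), power 80% (z = 0.842), uptake 0.60, ICC 0.01, the number 65, and 14,625 per arm. Equal allocation and equal cluster sizes are assumed, since neither is stated.

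**Step 1. Sample size without clustering.**

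n = (1.645 + 0.842)² × (0.0024 × 0.9976 + 0.0048 × 0.9952) / 0.0024² = 7,697 screened per arm (7,699 with the pooled-variance formula). Dividing by 0.6 gives about 12,829 invited.

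**Step 2. Room left for clustering.**

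14,625 × 0.6 = 8,775 screened per arm. The largest design effect compatible with 80% power is 8,775 / 7,697 = 1.14.

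**Step 3. Trying to reproduce 14,625.**

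With K clusters per arm, the screenees needed per cluster are m = n(1 − ICC) / (K − n × ICC). This has a solution only if K > n × ICC.

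- ICC 0.01: n × ICC = 77, above both 65 and 32.5. There is no solution, whether 65 is the count per arm or in total.
- 65 screenees per cluster, ICC 0.01: design effect 1 + 64 × 0.01 = 1.64, so 7,697 × 1.64 / 0.6 = 21,039 per arm.
- 65 invited and 39 screened per cluster, ICC 0.01: design effect 1 + 38 × 0.01 = 1.38, so 7,697 × 1.38 / 0.6 = 17,704 per arm.
- ICC 0.001 and 65 clusters in each arm: m = 7,697 × 0.999 / (65 − 7.7) = 134.2, rounded up to 135. Then 135 × 65 = 8,775, and 8,775 / 0.6 = 14,625 exactly.

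The two persons-per-cluster readings also conflict with the township count. At 14,625 per arm they imply 8,775 / 65 = 135 or 14,625 / 65 = 225 clusters per arm, against 65 townships in all.

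**Step 4. Power at 14,625 per arm.**

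Design effect = 1 + (m − 1) × ICC; effective n = screened / design effect; power = Φ(0.0024 / √(0.007171 / effective n) − 1.645). The ceiling uses effective n = K/ICC. The four-arm rows compare two-day with one-day sampling, pooling the two intervals (29,250 invited and 17,550 screened per side).

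| Reading | m | Design effect | Effective n | Power | Ceiling |
|---|---|---|---|---|---|
| ICC 0.01, 65 townships in total, two arms | 270 | 3.69 | 2,378 | 40% | 49% |
| ICC 0.01, 65 townships in total, four arms, pooled | 540 | 6.39 | 2,746 | 44% | 49% |
| ICC 0.01, 65 townships in total, one pair of four arms | 540 | 6.39 | 1,373 | 28% | 31% |
| ICC 0.01, 65 townships in each arm | 135 | 2.34 | 3,750 | 54% | 74% |
| ICC 0.01, 65 screened per cluster | 65 | 1.64 | 5,351 | 67% | n/a |
| ICC 0.01, 65 invited, 39 screened per cluster | 39 | 1.38 | 6,359 | 73% | n/a |
| ICC 0.001, 65 townships in total, two arms | 270 | 1.269 | 6,915 | 76% | above 99% |
| ICC 0.001, 65 townships in total, four arms, pooled | 540 | 1.539 | 11,404 | 92% | above 99% |
| ICC 0.001, 65 townships in each arm | 135 | 1.134 | 7,738 | 80.2% | above 99% |

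For the first row, the cap on effective n is 32.5 / 0.01 = 3,250, against 7,697 needed. Reaching 80% at ICC 0.01 takes more than 77 townships per arm, or more than 154 in total.

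**Step 5. Checks.** A beta-binomial simulation with a one-sided cluster-level t-test gives power of about 0.42 (ICC 0.01, 65 townships in total, two arms), 0.77 (ICC 0.001, same layout) and 0.81 (ICC 0.001, 65 per arm). At ICC 0.01 with 20,000 screenees in every township it is still only about 0.53.

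For two arms of 14,625 sharing 65 townships, 80% power needs 1 + 269 × ICC ≤ 1.14, so ICC of about 0.0005 or less.

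**The case against.** The strongest reply is that the ICC is simply misprinted. The exact match at 0.001 points that way, and so does plausibility. The between-township standard deviation implied by an ICC, relative to the mean rate, is √(ICC × p(1 − p)) / p. At ICC 0.01 that is 204% at 2.4 per 1000 and 144% at 4.8 per 1000; at 0.001 it is 64% and 46%. If 0.001 was used, two arms have 76% power rather than 40%, and the pooled comparison in a four-arm trial has 92%, above the target.

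This has weight, and it is why the 40% and the 49% ceiling hold only for the ICC as printed. It does not rescue section 1.5. The 0.001 is an inference from one exact match, and nothing in the documents shows which input is in error. Correcting the ICC alone still leaves two arms short of 80%, because the match also needs 65 townships in each arm. The 92% needs four arms of 14,625, which section 1.6 does not describe.

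A second reply is that section 1.6 reads as individual allocation of consenting people. If people were allocated within townships, this design effect would not apply and power at 8,775 screened per arm would be about 84%. No section says outright that whole townships are allocated, and the design figure is not available here. But sections 1.1, 1.3 and 1.4 all describe a clustered trial, and section 1.5 applies an ICC. If allocation is in fact individual, section 1.5 needs rewriting for that reason instead.

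**Conclusion.** The concern holds. The sample size cannot be derived from its stated inputs on any reading of 65, and none of those readings at ICC 0.01 gives more than 73% power at 14,625 per arm. Taking 65 as what the parenthesis says it is, with two equal arms and township-level allocation, power is about 40% and cannot exceed 49%.

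The most likely origin is an ICC of 0.001 combined with a trial-wide township count used as a per-arm count. In that case the shortfall for two arms is about four percentage points (76% against 80%), and a four-arm pooled comparison would meet the target. Which case applies cannot be settled from the documents. The formula results assume equal cluster sizes.

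**What to change.** Rewrite SAP section 1.5 to call 65 the total number of townships and to state the number of arms, townships per arm, mean screenees per township (270 with two arms of 14,625), the ICC actually used and the formula. State the unit of randomisation explicitly, and bring sections 1.4 and 1.6 into line on the number of arms. Then restate power:

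- **If the ICC was 0.001:** correct it, and report about 76% for two arms of 14,625, or about 92% for two-day against one-day sampling pooled over four arms of 14,625. If two arms must keep 80%, about 16,800 per arm are needed (m = 310; 310 × 32.5 / 0.6 ≈ 16,800).
- **If 0.01 is intended:** report about 40% for two arms or 44% for the four-arm pooled comparison. For two arms, the difference detectable with 80% power is about 7.4 against 2.4 per 1000. More people in the same townships would not restore 80%.

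The cost is one recalculation and a rewritten paragraph. No extra enrolment is needed to make the statement correct, but the power reported for two arms becomes less favourable.

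### SAP 1.5: the printed ICC of 0.01 implies implausible spread between townships for so rare an outcome and does not deliver the stated 80% power at 14,625 per arm; it may be a misprint of 0.001

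*SAP*

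**What the plan says.** SAP 1.5 is the only place where the sample size is justified. Its inputs are:

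- detection: "colorectal cancer detection rate of 2.4/1000 by one-sample FIT and 4.8/1000 by two-sample FIT";
- uptake: "FIT screening uptake rate of 60% in both arms";
- error rates: "80% power and one-tail significant level at 0.05";
- clustering: "cluster size of 65 (The total number of townships in Changhua, Tainan and Kaohsiung", combined with an "inter-cluster correlation coefficient of 0.01".

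The result is that "the estimated sample size is 14,625 subjects for each arm".

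The section says its assumptions draw on published work and national programme data. It gives no source or scale for the ICC, no township-level rates, no between-township variance and no number of clusters per arm. The 65 is called a cluster size but explained as a count of townships. SAP 1.1 and 1.3 describe cluster randomisation. SAP 1.4 lists four groups, and SAP 1.6 describes two arms.

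**The concern.** An ICC of 0.01 is modest for a common outcome. At 60% uptake it corresponds to a between-township SD of 4.9 percentage points. The same figure means something very different for an outcome of a few per 1000, because the variance it implies is large relative to so small a mean. Here the township rates would have an SD well above their own mean, although SAP 1.3 and 1.7 specify one age band, one assay and one cutoff.

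The stated 80% power is the plan's only assurance that the one-sample versus two-sample comparison can be answered. If 0.01 is the intended value, that power is not reached. If it is not, the document misreports the input, and anyone who repeats the calculation will reach the wrong view of the design.

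**Working it through.** **Inputs (all from SAP 1.5).** p1 = 0.0024, p2 = 0.0048, one-sided alpha 0.05, power 80%, uptake 0.60, ICC 0.01, 65 townships, 14,625 per arm. Tested per arm: 14,625 × 0.60 = 8,775.

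**1. Size before clustering.** With mean rate 0.0036 and difference 0.0024:

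n = [1.645·√(2 × 0.0036 × 0.9964) + 0.842·√(0.0024 × 0.9976 + 0.0048 × 0.9952)]² / 0.0024² ≈ 7,700 tested per arm.

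**2. Attempt to reproduce 14,625 with ICC 0.01.**

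- *65 people per cluster.* Design effect 1 + 64 × 0.01 = 1.64. Then 7,700 × 1.64 = 12,628 tested, and 12,628 / 0.6 = 21,047 invited. Neither is 14,625. With a continuity correction the figures are 13,961 and 23,269, which also miss.
- *65 clusters per arm.* People needed per cluster: m = n(1 − ICC)/(k − n·ICC). The denominator is 65 − 77 = −12, so no cluster size is large enough.

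**3. Attempt with ICC 0.001 and 65 clusters per arm.** m = 7,700 × 0.999 / (65 − 7.7) = 134.25, rounded up to 135. Then 65 × 135 = 8,775 tested, and 8,775 / 0.6 = 14,625 exactly. With 65 clusters per arm, only ICCs between about 0.00099 and 0.00104 give m = 135.

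**4. Township spread implied by the ICC.** SD = √(ICC·p(1 − p)) and CV = √(ICC·(1 − p)/p).

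| ICC | Mean per 1000 | SD per 1000 | CV |
|---|---|---|---|
| 0.01 | 2.4 | 4.9 | 2.04 |
| 0.01 | 4.8 | 6.9 | 1.44 |
| 0.001 | 2.4 | 1.5 | 0.64 |
| 0.001 | 4.8 | 2.2 | 0.46 |

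As an illustration, a beta distribution with mean 2.4 per 1000 and ICC 0.01 has a median township rate of about 0.4 per 1000. Some 37% of townships lie below 0.1, and the 95th percentile is about 11.8.

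**5. Ceiling on effective sample at ICC 0.01.** With k clusters per arm, km/(1 + (m − 1)·ICC) approaches k/ICC as m grows. That is 65/0.01 = 6,500, 32.5/0.01 = 3,250 or 16.25/0.01 = 1,625, all below 7,700. Power at these ceilings is about 74%, 49% and 31%, however many people are enrolled.

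**6. Power at 8,775 tested per arm.** The effective sample is 8,775/(1 + (m − 1)·ICC), entered in the formula of step 1.

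| Clusters per arm | m tested | Power, ICC 0.01 | Power, ICC 0.001 |
|---|---|---|---|
| 65 | 135 | 54% | 80% |
| 32.5 (65 townships over two arms) | 270 | 40% | 76% |
| 16.25 (65 over four groups, one group against another) | 540 | 28% | 69% |

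If 65 is people per cluster, the effective sample at ICC 0.01 is 8,775/1.64 = 5,351 and power is about 67%.

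**7. Pooling two of the four groups on each side.** At 14,625 per group this gives about 32 townships and 17,550 tested per side. Simulation of a township-level one-sided t-test gives about 91% at ICC 0.001 and about 47% at ICC 0.01.

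**The case against.** Several points on the other side have force.

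- **The pair is not impossible.** A reader might infer that an ICC of 0.01 cannot coexist with these rates. The beta distribution in the working has exactly that mean and ICC, and the documents contain no township rates that exclude it. Implausible and unsupported is as far as they allow one to go.
- **An ICC that is too high errs on the safe side.** A reader might infer that any power figure built on 0.01 is wrong or flattering. If 0.01 overstates the correlation, it understates power.
- **The 80% probably never rested on 0.01.** The exact match at 0.001 points that way, and at 0.001 the CV falls to 0.46–0.64. This stands as the likeliest explanation, but it is an inference. A few other combinations also land on or near 14,625, though each needs inputs that SAP 1.5 does not state.
- **The low cluster counts are assumptions.** SAP 1.3, 1.4 and 1.6 speak of participants or subjects being allocated. If every township contributed to both arms, much of the between-township variance would cancel and the ceilings would not apply. The 16-per-arm figures also compare one single group with another, whereas SAP 1.5 contrasts one-sample with two-sample testing and the four groups could be pooled.
- **14,625 might count people tested.** With 65 people per cluster, 14,625/1.64 = 8,918 then exceeds 7,700. But the calculation would have given 12,628, not 14,625, and SAP 1.5 defines 65 as a number of townships. The 6,500 ceiling for 65 clusters per arm does not depend on how the 14,625 are counted.

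These points limit the finding but do not remove it. On the clustered design as SAP 1.5 sets it out, the printed ICC and the printed power do not agree.

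**Conclusion.** The point holds in this form: in SAP 1.5 the printed ICC and the stated 80% power at 14,625 per arm cannot both stand. The ICC also implies township CVs of about 2.0 and 1.4, for which the documents offer no support. At ICC 0.01 and 8,775 tested per arm, power is about 28% to 67%, depending on how 65 is read and how many clusters each arm has. With 65 or fewer clusters per arm, 80% is out of reach at any enrolment.

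These figures assume the proportion-scale ICC, equal cluster sizes, equal allocation, 60% uptake applied to the 14,625 and, for the cluster-count figures, whole clusters allocated to one arm.

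A reader might go on to infer that the trial is badly underpowered. The documents do not support that. If 0.001 was the value used, power at the stated size is about 69% to 80% across the same cluster counts, and about 91% if groups are pooled. What the plan fails to show is which of these applies. The misprint is probable, not established.

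**What to change.** In SAP 1.5:

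1. Replace 0.01 with the ICC actually used for the 14,625, and give its scale and source. If 0.01 was intended, correct the stated power instead.
2. Check that ICC against the between-township CV it implies, √(ICC·(1 − p)/p), using national programme data where available. This applies to 0.001 as well, since a CV of 0.46–0.64 also needs support.
3. State whether whole townships are randomised, what the 65 denotes, and how many clusters lie on each side of the one-sample versus two-sample comparison, including whether the four groups are pooled for it.
4. Restate power at 14,625 per arm for that ICC and a plausible range around it.

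The cost is a wording change and a recalculation. The fix itself requires no change in enrolment. The downside is that the restated power may be less favourable than 80%: at ICC 0.001 it would be about 76% with about 32 clusters per arm and 69% with about 16.

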## **1.6 Selecting and inviting the population to be screened**

Initially, men and women between the ages of 50 and 69 will be identified and screened for eligibility and interest. Those who fulfill the eligibility criteria and are interested will be recruited into the trial and must provide a signed informed consent form. Participants will be randomly assigned into one of two study arms: the one-day sampling group and the two-day sampling group. Baseline data collection for participants in both arms of the trial includes completion of a questionnaire which collects basic demographic data and risk factor information. Invitation list will be generated by each site, based on the household registry in the individual region.

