## 1.4 Study groups, randomisation, and stratification

Subjects who meet inclusion/exclusion criteria will be randomized to 4 groups in

Confidential

this stratified, clustered randomized trial:

1. FIT one-day sampling with one-year interval
2. FIT one-day sampling with two-year interval
3. FIT two-day sampling with one-year interval
4. FIT two-day sampling with two-year interval

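### The abstract and SAP disagree on the unit of randomisation and the number of arms, and both the participation comparison and the stated 80% power depend on the answer

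*SAP*

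**What the plan says.** **Unit.** SAP 1.1 and 1.3 call the trial clustered or cluster-randomised, and 1.4 calls it "this stratified, clustered randomized trial". The same section 1.4 begins "Subjects who meet inclusion/exclusion criteria will be randomized to 4 groups in". The protocol abstract allocates people who attend screening, and SAP 1.3 and 1.6 allocate participants. Townships appear only in the sample-size sentence of 1.5: "taking into account cluster size of 65 (The total number of townships in Changhua, Tainan and Kaohsiung".

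**Number of arms.** The abstract and SAP 1.4 list four: one or two days of sampling, crossed with a one- or two-year interval. SAP 1.6 has two: "Participants will be randomly assigned into one of two study arms: the one-day sampling group and the two-day sampling group". SAP 1.5 also uses two-arm wording, "with a FIT screening uptake rate of 60% in both arms", and concludes "with inter-cluster correlation coefficient of 0.01, the estimated sample size is 14,625 subjects for each arm".

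**Recruitment.** SAP 1.6 is the only place that sets out a sequence. People are identified and their interest and eligibility are checked. The next step reads "Those who fulfill the eligibility criteria and are interested will be recruited into the trial and must provide a signed informed consent form", and assignment follows. It also says "Invitation list will be generated by each site, based on the household registry in the individual region", without placing that list in the sequence.

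**Participation.** The abstract treats it as an open question whether extra samples or a shorter interval reduce compliance or public participation. It lists participation rate first among the outcomes to be compared across the four groups. No section calls it primary or gives its denominator.

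**The concern.** A cluster trial and a consent-then-randomise trial of individuals support different comparisons.

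- If consent comes first, as 1.6 is written, people who are not interested or do not sign are never assigned. Participation by arm then has no invited denominator, and no later analysis can supply one.
- If clusters are allocated first, everyone on the invitation list in a cluster has an arm and participation can be compared. But those who consent may then differ between arms, so detection per consented or screened person is open to selection bias.

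The unit also fixes the design effect, and the number of arms fixes whether 14,625 for each arm means 29,250 or 58,500 people in total. Cancer detection is the only outcome with a power calculation, so whether its 80% holds depends on points the text leaves open.

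**Working it through.** **Inputs, all from SAP 1.5:** detection 2.4 and 4.8 per 1,000; one-sided 5%; 80% power; uptake 60%; ICC 0.01; the figure 65; 14,625 per arm.

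**Size needed without clustering.** With p1 = 0.0024, p2 = 0.0048 and mean p = 0.0036,

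n = [1.645 × √(2 × 0.0036 × 0.9964) + 0.842 × √(0.0024 × 0.9976 + 0.0048 × 0.9952)]² / 0.0024² ≈ 7,700 screened per arm.

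**The plan's own figure.** Reading 65 as cluster size, the design effect is 1 + 64 × 0.01 = 1.64, and 7,700 × 1.64 / 0.60 = 21,047 per arm, not 14,625. Leaving clustering out gives 7,700 / 0.60 = 12,833, or 8,513 / 0.60 ≈ 14,189 with a continuity correction, which is within about 3%. So 14,625 is not reproduced from all its stated inputs. That is a separate matter; the power figures below take 14,625 as given.

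**Power at 14,625 per arm.** If 60% of those allocated are screened, 14,625 × 0.60 = 8,775 per arm. Effective n is screened n divided by the design effect, and

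power = Φ{[0.0024 × √n_eff − 1.645 × √(2 × 0.0036 × 0.9964)] / √(0.0024 × 0.9976 + 0.0048 × 0.9952)}.

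| Reading | Design effect | Effective n per arm | Power |
|---|---|---|---|
| Individuals randomised | 1 | 8,775 | 84.4% |
| Two arms, 65 = invitees per cluster (39 screened) | 1 + 38 × 0.01 = 1.38 | 6,359 | 73.1% |
| Two arms, 65 = screened per cluster | 1.64 | 5,351 | 66.6% |
| Two arms, 65 townships in all (2 × 8,775 / 65 = 270 screened each) | 1 + 269 × 0.01 = 3.69 | 2,378 | 39.6% |
| Four groups pooled by sampling (17,550 per margin), 65 = screened per cluster | 1.64 | 10,701 | 90.1% |
| Four groups pooled by sampling, 65 townships in all (4 × 8,775 / 65 = 540 screened each) | 1 + 539 × 0.01 = 6.39 | 2,746 | 43.6% |

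**Ceiling with 65 townships.** As enrolment per township grows, effective n per arm approaches 32.5 / 0.01 = 3,250, against 7,700 needed. Power then stops at about 48.8%, however many people are enrolled and whatever the uptake.

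**Participation, by logic rather than arithmetic.** Under 1.6, the people who hold an arm are those who were eligible, interested and consenting. Kit return and repeat-round compliance have that denominator in each arm. The share of invited people who take part does not, because those who declined were never assigned.

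**The case against.** The strongest reply is that this is loose drafting of one coherent design. The four groups in 1.4 are plainly a 2 × 2 layout, and the two arms in 1.5 and 1.6 could be its sampling margins. That is plausible, but no available section says so. Figure 4-1, the design schematic, is not shown in the text available here and may settle unit, flow and arms; what it contains cannot be counted as missing. It would not remove the conflicting wording. The one-sample and two-sample positivity rules in 1.7 depend only on the number of samples and would read the same with four groups, so they are not evidence of two arms.

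On participation, the reply is that decliners have no arm in any trial that randomises after consent, and that uptake among those allocated can still be compared. Both are true. The loss concerns participation as a share of those invited, which is the natural meaning of the abstract's public participation but is not defined there.

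Three stronger readings are tempting and not supported:

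- *That the documents contradict each other on the order of consent and allocation.* No section puts allocation before consent. The abstract, 1.3 and 1.4 are compatible with the sequence in 1.6; the tension is with the cluster label.
- *That the plan declares townships allocated before contact.* It does not. Townships are never named as the randomised unit, nor is their allocation timed.
- *That power is simply 40%.* That holds only for 65 townships split between two arms at ICC 0.01. The literal wording makes 65 a cluster size, which gives 67% or 73% with two arms and about 90% with four pooled groups. In addition, 14,625 = 65 × 225 would fit every township contributing to every arm, and the township ceiling would then not apply as stated. That is inference too. A smaller ICC also raises the township figure: an assumed 0.001 gives about 76% with two arms.

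**Conclusion.** The contradictions on unit and on number of arms are in the current text. If 1.6 is followed literally, participation among invited people cannot be compared by arm, and only compliance among consenters can. If clusters are allocated first, participation can be compared, but detection among consenters is open to selection.

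Power for cancer detection runs from about 40% to about 90% across the readings tabulated. The stated 80% is met with individual randomisation (84%) and with four pooled groups in clusters of 65 screened (90%). It is not met with two arms and 65 as a cluster size (67% to 73%), or with 65 townships as the randomised clusters (40% with two arms, 44% with four, ceiling 49%).

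These figures assume equal cluster sizes, an ICC of 0.01 for cancer detection, and 60% as a share of those allocated, which 1.5 does not say; the ceiling does not depend on the 60%. The contradictions are certain. Which design was intended is not, and the documents do not allow the choice to be made for the sponsor.

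**What to change.** - Reconcile the abstract and SAP 1.1 to 1.6 to one randomisation unit, one order of invitation, consent and allocation, and one number of arms. The sponsor should state which; the text does not settle it.
- Say whether the two arms in 1.5 and 1.6 are the pooled sampling margins of the four groups, and whether 14,625 is per margin or per group.
- Define the denominators of the participation rate and of the 60% uptake.
- If allocation precedes consent, keep counts of invited people by arm from the household-registry list, use them as the participation denominator, and report detection per invited person beside detection per screenee.
- If consent precedes allocation, limit the by-arm claim to compliance among consenters.
- Restate power with a design effect that matches the unit randomised, using 65 as either a cluster size or a number of clusters, not both.

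The cost is mainly wording, plus keeping the invited counts. The stated power may become less favourable, and the timing of consent may need confirmation from the ethics committee.
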